3.5. Randomization

This clinical trial will utilize simple randomization based on the technique described by (Oliveira et al., 2021). This method involves drawing envelopes to determine the following:

- Surgical site: Test or control side
- Tooth: Right third molar ("A") or left third molar ("B")
- Surgery order: First or second session

The following steps of randomization will be followed:

1. Draw the tooth: An envelope is drawn to determine which third molar will be extracted first (right or left).
2. Draw the intervention: A second envelope is drawn to determine whether the selected tooth will receive the test intervention ("X-1") or no intervention ("X-2").
3. Draw the surgery order: A final envelope is drawn to determine whether the selected tooth will be extracted in the first or second surgery session.

3.6.Pre-operative and Post-operative Assessment

Prior to surgical removal of impacted third molar, preoperative variables (i.e., pain, trismus, and facial swelling) will be taken for each patient and recorded in the data collection sheet. Furthermore, the same post-operative variables (preoperative variables) will be taken immediately after the procedure, 2nd day, 3rd day and 5th day after the operation. Both pre-operative and post-operative variables will be done by the same measurements.

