3.1. Study Design

This clinical trial will utilize a split-mouth design, randomly assigning two different treatments to each half of the patient's mouth. From this randomized study which is characterized by a triple-blind study, the procedures are going to be performed by qualified and experienced professional. However, the operator will have no access to data evaluated. The evaluator will have access to all responses of the symptoms of patients and will not know the treatment that is going to be selected, while the patient is unaware of which treatment or intervention is being applied to each side of their mouth. This stringent blinding approach minimizes potential biases and significantly enhances the scientific validity of the study.

Patients will be assigned into two groups and each patient acted as their own control using the split-mouth technique. One impacted third molar will be removed from one side and will receive conventional drugs while the other side will be removed after 3 weeks (wash-out period) and receive additional treatment beside the conventional drugs (i.e., either enzyme or herbal). The two groups will be classified as follows:

- The first group will receive conventional drugs with 10mg oral serratiopeptidase at immediate post-operative time and three times a day for post-operative five days on the first surgical visit and on the second surgical visit (after 3 weeks) conventional drugs will be given only or vice versa.
- The second group will receive conventional drugs with 20mg oral escin at immediate post-operative time and three times a day for post-operative five days on the first surgical visit and on the second surgical visit (after 3 weeks) conventional drugs will be given only or vice versa.

The conventional drugs, it will be administered to patients in the two groups, includes: Amoxicillin 500mg Cap b.i.d., Metronidazole 500mg Tab t.i.d., Diclofenac sodium 50mg Tab b.i.d.

3.2.Study Population

The study population will include patients who will visit the dental clinics in the College of Dentistry, University of Science and Technology, Yemen (USTY) for impacted mandibular third molars extraction during 2024.

3.3.Sample Size

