The sample size is the number of participants planned to be included in the trial, usually determined using a statistical power calculation (Zanatta et al., 2017). This study determined the sample size using a power calculation based on previous research by (Costa et al., 2015). Their study found that preemptive use of etoricoxib 120mg significantly reduced the need for rescue analgesic medication compared to a placebo (1.6 ± 1.3 vs 4.0 ± 2.5). To achieve a power of 80% and a confidence interval of 95%. The study will need to evaluate 11 surgical sites per sub-group (<http://www.openepi.com/SampleSize/SSMean.htm>). To account for a potential 20% drop-out rate, a total of 14 sites per sub-group will be recruited. This will result in a total sample size of 56 dental units (2 teeth per patient) from 28 patients. The following Table 3-1 illustrates the study sample size and the planned treatment.

Table 3-1 : Sample Size and Study Treatment.

Groups	I		II		Total
Patients	14		14		28
Sub-groups	Control 1	Study 1	Control 2	Study 2	4
Sample size	14	14	14	14	56
Conventional Treatment	Amoxicillin 500mg Cap b.i.d		Metronidazole 500mg Tab t.i.d		N/A
	Diclofenac sodium 50mg Tab b.i.d				
Study Treatment	N/A	Serratiopeptidase 10mg t.id	N/A	Escin 20mg t.id	N/A

3.4.Sample Selection

Patients who will undergo to surgical removal of the impacted third molar will be assessed for their eligibility to participate according to the following inclusion and exclusion criteria:

Inclusion criteria:

- Medically fit patients.
- The presence of two asymptomatic mandibular third molar indicated for surgical extraction.
- Absence of pericoronitis or signs of inflammation during the last 30 days

Exclusion criteria:

- Patient administered other drugs such as NSAIDS and steroids.
- Patient has allergy to the drugs used in this study.
- Pregnant patient or a patient with lactation.
- Immunocompromised patients with diabetic or hypertension (from patient's history).
- Patients with irradiated maxillofacial region.
- Intellectually disabled patients and patients unable to come for follow up visits.
- Patients with acute and subacute pericoronitis

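### No draw in section 3.5 assigns serratiopeptidase versus escin, so the between-drug comparison is not shown to be randomized and the 14:14 split has no mechanism

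*Combined protocol and SAP*

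**What the plan says.** Section 3.5 (Randomization) names the method, "This clinical trial will utilize simple randomization", and adds: "This method involves drawing envelopes to determine the following". The items listed are test or control side, right or left tooth, and first or second session. Three draws follow:

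- Draw 1: "An envelope is drawn to determine which third molar will be extracted first (right or left").
- Draw 2 decides whether that tooth gets the test intervention or none. It names neither drug.
- Draw 3: "A final envelope is drawn to determine whether the selected tooth will be extracted in the first or second surgery session".

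Section 3.1 (Study Design) covers the drug group in one sentence: "Patients will be assigned into two groups and each patient acted as their own control using the split-mouth technique". It gives no method. Its reference to random assignment concerns the two halves of one patient's mouth. The two group descriptions in 3.1 allow either treatment order, with no requirement that orders balance.

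Section 3.3 (Sample Size) says that "a total of 14 sites per sub-group will be recruited", and Table 3-1 shows 14 patients in Group I (serratiopeptidase) and 14 in Group II (escin). The general objective (1.4) and Hypothesis 3 (1.5) compare the two drugs. Section 3.9 plans a paired t test or Wilcoxon test, with no term for session.

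**The concern.** Each patient receives only one of the two study drugs. Serratiopeptidase versus escin is therefore a comparison between different patients, and the split-mouth design does not protect it. It needs random allocation to drug group, and the protocol describes none. Alternation, or filling Group I before Group II, would comply with the text and would leave the trial's overall objective resting on non-randomized groups.

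Two smaller matters sit in the same section. Unrestricted draws do not in general produce the fixed numbers in Table 3-1 or a balanced surgery order, and the planned paired test has no means of removing a session effect. The first and third draws also both bear on which tooth comes out first.

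**Working it through.** **1. What is randomized.** Setting 3.5 beside 1.5 and 3.1:

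| Element | Level | Draw in 3.5 |
|---|---|---|
| Right or left tooth | within patient | draw 1 |
| Test or no intervention | within patient | draw 2 |
| First or second session | within patient | draw 3 |
| Serratiopeptidase or escin | between patients | none |

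Hypotheses 1 and 2 rest on the first three rows. Hypothesis 3 rests on the last.

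**2. The plan's own sample size.** Inputs from 3.3: means 1.6 and 4.0, SDs 1.3 and 2.5, power 80%, two-sided 5%.

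n = (1.3² + 2.5²) × (1.960 + 0.842)² / 2.4² = 10.8, so 11. Then 11 / 0.8 = 13.75, so 14 per sub-group, 2 × 14 = 28 patients and 56 teeth. The stated figures reproduce.

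**3. Group sizes if simple randomization were extended to drug group (assumption: 28 independent fair draws).**

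- P(14:14) = C(28,14) / 2²⁸ = 0.149.
- P(smaller group ≤ 11) = 0.345.
- P(smaller group ≤ 10) = 0.185, that is, fewer than the 11 required even before dropout.
- With 13 patients and 20% dropout, 13 × 0.8 = 10.4 are expected to be evaluable.

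The loss from unequal sizes is small in itself: 18:10 keeps 4 × 18 × 10 / 28² = 92% of the efficiency of 14:14.

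**4. Surgery order within a group of 14 (fair independent draws).**

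- P(7:7) = C(14,7) / 2¹⁴ = 0.209; in both groups, 0.209² = 0.044.
- P(10:4 or worse) = 0.180.
- At 10:4, (10 − 4) / 14 = 43% of any session difference enters the mean paired difference.

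The documents give no session difference. Assuming one of 0.5, 1 or 2 SD of the paired difference, simulation with n = 14 gives:

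| Order and test | Type I error at 0.5 / 1 / 2 SD | Power for a 0.8 SD effect |
|---|---|---|
| Order drawn simply, paired t | 4.9% / 5.1% / 5.2% | 70% / 49% / 21% |
| Order forced 7:7, paired t | 2.9% / 0.6% / under 0.01% | 71% / 47% / under 5% |
| Order forced 7:7, session term | about 5% throughout | about 78% throughout |

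With 7:7 the session shift cancels from the mean difference but stays in its SD, so the plain paired test becomes conservative. A session term removes it from both. The 78% can be checked directly: noncentrality 0.8 × √14 = 2.99 on 14 − 2 = 12 degrees of freedom.

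**5. Draws 1 and 3.** Read literally, draw 1 selects the tooth that comes out first, and draw 3 then draws a session for that same tooth. If both are fair and independent, they conflict with probability 1/2.

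**The case against.** The strongest reply is that the 14:14 probabilities describe a procedure the protocol does not contain. That is right. Section 3.5 applies simple randomization to side, tooth and session only, so a reader who infers that the stated method will usually miss 14:14 goes further than the text. The gap is that no method is stated for the drug split; the binomial figures show only what would follow if the named method filled it. Drawing from a fixed pool of envelopes would force balance. The protocol describes no such pool, and the cited trial from which the technique is taken cannot be consulted here.

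Nor are all the sub-group sizes in doubt. Control and Study counts within a group are equal because each patient supplies both. Only the Group I to Group II split is open.

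A reader might also infer that order imbalance biases the treatment effect. The documents do not support that. Order is drawn at random, so a session effect averages to zero over repeated trials, and the paired t test carries it in its standard error; type I error stays near 5%. What stands is that it costs power and can shift the single estimate obtained.

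Draw 1 can be read as merely picking a tooth, which removes the conflict with draw 3, but its wording says otherwise.

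None of this supplies a random allocation to drug.

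**Conclusion.** The point holds and should be settled before the first patient is enrolled. No random allocation of serratiopeptidase versus escin is described, although the general objective and Hypothesis 3 depend on one and Table 3-1 presupposes its result. This rests on the text alone. It does not establish that the groups will be non-randomized in practice, only that the protocol permits it.

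The rest is secondary. The 15% chance of 14:14 and the 18% chance of fewer than 11 in one group are conditional on simple randomization being used for drug. The 18% chance of a 10:4 order split or worse assumes fair independent draws and exactly 14 in the group. Its cost is precision, of a size that depends on a session effect the documents do not give. Hypotheses 1 and 2, which are within-patient, remain randomized once draws 1 and 3 are reconciled.

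**What to change.** **Section 3.5.** Replace the three draws with one computer-generated list, made before enrolment, that assigns each of the 28 patients to one of four cells: drug (serratiopeptidase or escin) by order (drug first or control first), 7 per cell. Randomize side within cell. This gives 14:14 by drug and 7:7 by order within each drug, and it removes the conflict between draws 1 and 3.

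Use a single random permutation of 28, or varying block sizes that are not disclosed. With fixed blocks of 4, the last assignment in each block follows from the previous three, and no placebo is described that would keep those three hidden. Hold assignments in sequentially numbered, sealed, opaque envelopes, with the list withheld from the surgeon and evaluator. State in 3.1 that drug group is assigned from this list.

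**Section 3.9.** For each drug against its control, add a session term to the within-patient comparison; without it, balancing the order makes the paired test conservative. For Hypothesis 3, compare the within-patient differences (drug minus control) between the two groups.

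**Cost.** One list to prepare, one degree of freedom for the session term (12 instead of 13 with 14 patients), and slight predictability near the end of the list. The sample size stays at 28.

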2.1.5. Complications of the Removal of Impacted Third Molars

Possible complications of third molar removal include nerve numbness (paresthesia), dry socket (alveolar osteitis), infections, bleeding, jaw fracture, bone infection (osteomyelitis), damage to neighboring teeth, exposed fat pad in the cheek, opening between the mouth and sinus cavity (oral-antral communication), displaced teeth, inhaled objects (aspiration), gum tissue damage (periodontal defects), and jaw joint problems (temporomandibular joint injury). The four most common complications are nerve numbness, dry socket, infections, and bleeding (Bouloux et al., 2007).

While pain, swelling, and trismus are expected following surgery, poor surgical technique can exacerbate these issues. Pain management relies on analgesics administered before anesthesia wears off. Persistent pain indicates potential infection or dry socket requiring follow-up. Transdermal patches have shown effectiveness for post-extraction pain (Bhargava et al., 2019). Trismus may arise from injury to the medial pterygoid muscle or inflammation/hematoma at the extraction site (Fragiskos, 2007). Proper patient selection and surgical skill can minimize risks.

2.2. Post-operative Treatment following Third Molar Surgery.

Following third molar surgery, a course of conventional medication is typically prescribed to manage pain, swelling, and infection. Pain management commonly involves NSAIDs like ibuprofen or naproxen (Bhargava et al., 2019), while antibiotics may be employed to prevent or treat infection (Malamed, 2019). Additionally, corticosteroids may be used to combat inflammation and reduce swelling (Undrell Moore, 2011). To ensure optimal healing and minimize discomfort, adhering to the prescribed medication regimen and following post-operative instructions are crucial (Wayland, 2024).

Emerging research suggests potential benefits for both enzymes and phytotherapeutic drugs in managing post-surgical pain and swelling. Serratiopeptidase, a proteolytic enzyme, has shown promise in reducing inflammation around teeth and implants, potentially offering similar benefits after third molar extraction (Sannino et al., 2013; Villafuerte-Nuñez et al., 2013). Escin, a phytotherapeutic drug derived from horse chestnut, exhibits potent anti-inflammatory properties, suggesting its potential in reducing post-surgical inflammation and swelling (Wang et al., 2009). Figure 2-6 summarizes and compares between both medicines as follows:

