Feature	Serratiopeptidase	Escin
Chemical Structure	Zinc-containing protein (metalloprotease)	Mixture of triterpenic glycosides
Source	Enterobacterium Serratia	Horse chestnut seeds
Pharmacokinetics	Limited absorption through intestines, distributed to sites of inflammation	High concentrations in skin and muscle, minimal internal distribution
Pharmacodynamics	Anti-inflammatory, analgesic, fibrinolytic, anti-biofilm, wound healing	Anti-edematous, anti-inflammatory, venotonic
Administration	Oral tablets	Oral tablets, topical gels/creams
Dosage	10-60 mg/day (2000 units/mg)	20 mg/day (oral), 1-2 applications/day (topical)
Complications	Rare adverse reactions like Stevens-Johnson syndrome, esophageal ulcers	Hepatic injury, toxic nephropathy
Contraindications	Pregnancy, breastfeeding, hemophilia, liver/kidney dysfunction, concurrent use with antiplatelet drugs/anticoagulants/natural supplements	Pregnancy, breastfeeding, renal/hepatic impairment
Therapeutic Applications	Oral and maxillofacial surgery (post-operative pain/swelling), inflammation, infections, major surgeries, traumatic injuries	Chronic venous insufficiency, hemorrhoids, post-operative edema, cerebral/intracranial edema, gynecology, periodontitis

Figure 2-1 Serratiopeptidase vs. Escin: A Comparative Table.

2.3.Split-mouth Randomized Controlled Trials

Dental clinical trials offer two options for randomizing treatments: over individuals (mouth-level) or over sites within the mouth (site-level). The parallel-group design, where the same treatment is applied throughout the entire mouth, is the simplest and most commonly used approach. On the other hand, the split-mouth design involves random assignment of treatments to specific sites within the mouth. This design utilizes each person as their own control, allowing for more precise treatment comparisons

(Lesaffre et al., 2009). The split-mouth design was introduced by (Ramfjord et al., 1968) to compare the effectiveness of different periodontal therapies within each subject's mouth. The design divides the mouth into two halves, randomly assigning different treatments to each half.

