Appendix A: Case Sheet

[figure not shown]
PERSONAL DETAILS	
Case no.	
Name of patient	
Age	
Sex	
Occupation	
Contact no.	
Address	

MEDICAL STATUS	
Chief complaint& duration	
History of presenting illness	
Medical history	
Dental history	
Oral hygiene	

IMPACTED THIRD MOLARS DETAILS		
Characteristics	First visit	Second visit
Group: I/II		
Sub-group: C/S		
Side: R/L		
Depth: A/B/C		
Angulation: H/M/D/V		
Position: Class I/Class II/Class III		

SURGICAL DETAILS		
Characteristics	First visit	Second visit
Date of surgery		
Number of dental cartridges		
Duration of surgery: min		
Bone removal: mild/moderate/sever		
Tooth sectioning: yes/no		

SURGICAL ASSESSMENT – FIRST VISIT		Pre Operative	Immediate	2 nd Day	3 rd Day	5 th Day
Mouth Opening	Trismus					
Facial Swelling	From tragus of ear to corner of mouth					
	From tragus of ear to soft tissue pogonion					
	From lateral canthus of eye to angle of mandible					
Pain	 
A horizontal scale from 0 to 10. The scale is color-coded: green for 0-3, yellow for 4-6, and red for 7-10. Below the scale are six faces representing pain levels: 0 (smiling), 1-3 (mild smile), 4-6 (neutral), 7-9 (frowny), and 10 (crying). The text 'No Pain' is above the 0 mark, and 'Worst Pain Possible' is above the 10 mark.
					

SURGICAL ASSESSMENT – SECOND VISIT		Pre Operative	Immediate	2 nd Day	3 rd Day	5 th Day
Mouth Opening	Trismus					
Facial Swelling	From tragus of ear to corner of mouth					
	From tragus of ear to soft tissue pogonion					
	From lateral canthus of eye to angle of mandible					
Pain	 
A horizontal scale from 0 to 10. The scale is color-coded: green for 0-3, yellow for 4-6, and red for 7-10. Below the scale are six faces representing pain levels: 0 (smiling), 1-3 (mild smile), 4-6 (neutral), 7-9 (frowny), and 10 (crying). The text 'No Pain' is above the 0 mark, and 'Worst Pain Possible' is above the 10 mark.

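### Apart from pain, trismus and swelling, complications and drug reactions have no recording field, so zero reports could not be read as zero events

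*Combined protocol and SAP*

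**What the plan says.** Section 3.6 names what is measured before surgery: "preoperative variables (i.e., pain, trismus, and facial swelling) will be taken for each patient and recorded in the data collection sheet". After surgery, "the same post-operative variables (preoperative variables) will be taken immediately after the procedure, 2nd day, 3rd day and 5th day after the operation". The grid in Appendix A under "SURGICAL ASSESSMENT – FIRST VISIT", and its second-visit twin, has rows for mouth opening, three facial lines and pain. The surgical-details block records date, cartridges, duration, bone removal and sectioning. Section 3.9 analyses the three efficacy variables and nothing else.

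Other complications appear as background. Section 2.1.5 states: "The four most common complications are nerve numbness, dry socket, infections, and bleeding". It adds: "Trismus may arise from injury to the medial pterygoid muscle or inflammation/hematoma at the extraction site". Figure 2-1 gives the pharmacodynamics of serratiopeptidase as "Anti-inflammatory, analgesic, fibrinolytic, anti-biofilm, wound healing" and its complications as "Rare adverse reactions like Stevens-Johnson syndrome, esophageal ulcers". For escin it lists liver injury and toxic nephropathy.

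Section 3.1 sets group I's add-on as "10mg oral serratiopeptidase at immediate post-operative time and three times a day for post-operative five days", alongside diclofenac and two antibiotics, after one of each patient's two surgeries. Group II receives escin in the same pattern.

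Section 3.7 tells patients about possible complications, asks them to contact the surgeon if issues arise, and requests that they report physical symptoms during the study. Section 3.1 gives the evaluator access to symptom responses.

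**The concern.** The protocol lists four common surgical complications and names adverse reactions for both add-on drugs. None of these has a place on the form, apart from any overlap with the three efficacy outcomes. Whether an event enters the record depends on the patient raising it and on someone writing it down somewhere unspecified.

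What is at stake is the safety statement, not the efficacy comparison. Section 1.1 motivates the add-ons partly as alternatives that may have fewer side effects than corticosteroids and NSAIDs. A report that no adverse events occurred would be natural at the end of this trial. Under passive reporting, it could not be told apart from events that occurred and went unrecorded. Analysts cannot rebuild the record after the visits.

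**Working it through.** **Recording, item by item**

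- Pain, mouth opening, swelling: scheduled in 3.6, gridded in Appendix A, analysed in 3.9.
- Bleeding or haematoma, dry socket, infection, numbness: named in 2.1.5; absent from 3.6, the visible Appendix A and 3.9.
- Drug reactions: named in Figure 2-1; absent from the same three places.
- Only route for the last two groups: the open request in 3.7, with no definition, form, time point or tabulation.

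**Denominators**

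The sample size in section 3.3 uses means 1.6 and 4.0, SDs 1.3 and 2.5, 80% power and two-sided 5%:

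n = (1.960 + 0.842)² × (1.3² + 2.5²) / 2.4² = 7.849 × 7.94 / 5.76 = 10.82, so 11 per sub-group. Then 11 / 0.80 = 13.75, so 14.

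Both match the plan. The number of study sessions assessed in each group will therefore lie between 14 (no loss) and about 11 (planned 20% loss).

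**What zero events would mean if every session is examined**

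One-sided 95% upper bound = 1 − 0.05^(1/n).

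- n = 14: 19.3%
- n = 11: 23.8%

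**What zero reports would mean under passive reporting**

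The documents give no reporting fraction. Let c be the assumed share of events that reach the record. The bound on the true rate becomes the figure above divided by c.

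| c (assumed) | n = 14 | n = 11 |
|---|---|---|
| 1.00 | 19.3% | 23.8% |
| 0.75 | 25.7% | 31.8% |
| 0.50 | 38.5% | 47.7% |
| 0.25 | 77.1% | 95.4% |

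The chance of recording at least one event in 14 sessions is 1 − (1 − c·p)^14. For c = 1, 0.75, 0.50 and 0.25:

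- assumed true rate p = 10%: 77%, 66%, 51%, 30%
- assumed true rate p = 5%: 51%, 41%, 30%, 16%

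These rows show how under-reporting works. They do not estimate the loss in this trial, because c and p are not known. That is the difficulty: with c unknown, zero reports carry no usable bound.

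**Whether a test would be worthwhile**

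For an exact McNemar test with no control-only events, 5 study-only events give p = 2 × 0.5⁵ = 0.0625 and 6 give p = 2 × 0.5⁶ = 0.031. So at least 6 of 14 pairs must be discordant, all in one direction. At assumed rates of 20% and 5%, with sessions independent within patient, power is about 2% (n = 14). Only descriptive reporting is realistic.

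**The case against.** The strongest reply is that little hangs on this. The objectives and hypotheses are efficacy only, no planned conclusion changes, and even complete ascertainment leaves a bound near 20%. All of that stands, and it limits the point to an inexpensive improvement.

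The text available is also incomplete. Appendix A opens with a figure that is not shown, Appendices B and C were not available, and the standardized form returned at suture removal (section 3.6.1) is not reproduced. Both assessment grids look complete, however, and the only content stated for that form is pain scores. This lowers certainty slightly and does not remove the gap.

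A reader might infer more than the documents support:

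- *That there is no safety reporting at all.* Section 3.7 asks for symptoms and section 3.1 gives the evaluator access to responses. Reporting exists but is unstructured. The protocol also counts pain, trismus and swelling as complications, and these are recorded well.
- *That study and control counts would differ through reporting.* Control sessions receive conventional drugs only and no placebo is described, so a patient might notice extra tablets. But section 3.1 states that patient and evaluator are unaware of treatment, and nothing shows that reporting would differ. Under-counting is supported; differential counting is not.
- *That haematoma biases the efficacy comparison.* A haematoma caused by the add-on is part of its net effect on swelling and mouth opening.
- *That serratiopeptidase with diclofenac is contraindicated.* The documents do not say so, and the complications entry in Figure 2-1 does not list bleeding for serratiopeptidase. The fibrinolytic label makes bleeding a sensible event to look for, no more.

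**Conclusion.** The gap is real and small. Outside the three efficacy outcomes, complications and drug reactions would be captured passively and probably incompletely in both groups, and an absence of reports could not be read as an absence of events. Structured recording would make a zero count interpretable, as excluding true rates above about 19% to 24% per sub-group, and would make any observed events countable by treatment and session. It would not support a comparison. The bounds rest on the plan's 14 sessions, or about 11 after drop-out, and on every assessed session being examined. The capture fractions and event rates used to illustrate passive reporting are assumptions. This is an optional, inexpensive improvement, available only if adopted before the visits take place.

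**What to change.** Add two rows to both assessment tables in Appendix A, and one sentence each to sections 3.6 and 3.9:

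1. Bleeding or haematoma beyond normal ooze (defined in writing before the first surgery): none / present / needed treatment.
2. Other complication or suspected drug reaction (infection, dry socket, persistent numbness, rash, gastrointestinal or other symptoms): none / describe.

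The blinded evaluator completes both on days 2, 3 and 5 of each session, by inspection and one standard question. Make no numbness entry at the immediate assessment, while the nerve block is active. Repeat the question at suture removal and, for the first session, at the second-surgery visit. This reaches events after day 5, when dosing ends. Show the second-surgery answers separately, because the second session has no matching visit.

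Tabulate the worst grade by treatment and by session within groups I and II. Use the sessions actually assessed as the denominator, and give the zero-event bound where it applies. Run no test, and exclude no session from the paired efficacy analysis.

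Cost: 2 rows × 3 days × 2 sessions = 12 entries per patient, plus 3 repeat questions (two at suture removal, one at the second surgery). Over 28 patients that is 336 entries and 84 questions, plus one small table. Mouth opening and swelling already need in-person measurement on days 2, 3 and 5, so no visit, procedure or staff is added. The downside is data too sparse for inference.
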